8.9. PREGNANCY

If a female participant or the spouse of a male participant becomes pregnant during the trial, this is recorded and reported to the ethical and regulatory authorities and the sponsor. If the pregnancy is discovered during the treatment period, the use of the trial drug should be discontinued and the pregnancy event should be reported in the eCRF. If the pregnancy is discovered during the follow-up period, it should also be reported in the eCRF. If the pregnancy occurs within 6 months after the end of the trial, the pregnancy event should be reported to the sponsor and ethical and regulatory authorities. In all cases, the mother and baby should be followed up until delivery. Pregnancy complications and selective termination of pregnancy for medical reasons should be reported as AE or SAE, and spontaneous abortion should be reported as SAE.

8.10. NOTIFICATION OF AE

AEs, SAEs, and SUSARs should be recorded in detail in source documents and in the participant's eCRF, in accordance withMedDRA terminology (version 23.0) to specify the event that occurred.

The Principal Investigator must notify the sponsor of the occurrence of AEs in a timely manner. Non-serious AEs should be reported to the ethical and regulatory authorities in the follow-up reports of the investigational medicinal product.

The Principal Investigator must notify the sponsor of the occurrence of SAE or SUSAR within 24 hours of knowledge of it, in a dated and signed document, regardless of the causal relationship to the trial drug. Additional information should be reported as soon as available. The sponsor must report the occurrence of unexpected, possible, probable or definite SAEs to the regulatory and ethical authorities within 7 calendar days¹⁷.

For SAE or SUSAR whose information is temporarily incomplete and uncertain, it should also be reported in a timely manner, and should be reported in the form of a follow-up report to the regulatory authorities after more information is obtained.

9. CONCLUSION AND DISCONTINUATION OF THE STUDY

Information about the completion or discontinuation of the trial research participant and the reason for study discontinuation will be recorded in the appropriate CRF.

9.1. CONCLUSION OF THE PARTICIPANT

At the end of the treatment period of up to 14 days or when the coronavirus viral load detection by RT-PCR is negative on two consecutive occasions, considering a difference of at least 24 hours between the two sample collections, the study medication

will be discontinued and the participant continues with the standard treatment therapy. Treatment may also be discontinued if the Principal Investigator deems it best for the participant's safety, or if the participant decides not to continue with treatment. In either situation, follow-up will be done on days D28 and D60 after the end of treatment.

The participant will only be discharged from the hospital at the end of treatment after medical evaluation by the Principal Investigator. The participant will be required to return to the hospital for follow-up visits. After the last visit, the subject's participation in the study will be considered terminated.

The need for additional intervention or the occurrence of safety endpoints/endpoints do not constitute trial completion and are not criteria for withdrawal from the trial or the trial medication.

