1. SUMMARY

1.1. SYNOPSIS

	Evaluation of the Safety and Clinical Efficacy of AZVUDINE in
TITLE	patients infected with SARS-CoV-2 virus: a Phase III,
	randomized, double-blind, PLACEBO-controlled study.
STUDY ID	IGZ-1
DOCUMENT TYPE	Phase III Clinical Trial Design
VERSION/ISSUANCE DATE	Version 0.5 of May 30, 2022
	HRH HOLDINGS LIMITED, [name]
SPONSOR	[name]
	[name].
	INSTITUTO GALZU DE PESQUISA, ENSINO, CIÊNCIA E
	TECNOLOGIA APLICADA, CNPJ: 28.831.817/0001-20.
	Office: [name], Zip Code:
REPRESENTATIVE	[name], Campos dos Goytacazes-RJ.
ORGANIZATION OF	Interface Hospitalar: [name],
CLINICAL RESEARCH	[name], Hospital Santa Casa de
SPONSOR IN BRAZIL (ORPC)	Misericórdia de Campos, [contact] Ext.
	180/194
	Contact [name] [name]
	Site: http://www.institutogalzu.org.br
	E-mail: [contact]
CTUDY CITE	Santa Casa de Misericórdia de Campos, Campos dos
STUDY SITE	Goytacazes - RJ

	Primary Goal
OBJECTIVE	 To evaluate the efficacy and safety of AZVUDINE (FNC) versus placebo in patients infected with moderate to severe stage SARS-COV-2; Secondary objective
	 To evaluate the clinical outcome between the AZVUDINE (FNC) group versus the PLACEBO group in patients infected with moderate to severe stage SARS- COV-2;
INTERVENTION	 Experimental group: AZVUDINE 5mg/day, orally for up to 14 days + Standard treatment. Control group: PLACEBO orally for up to 14 days + Standard treatment.
NUMBER OF PARTICIPANTS	Following initial study data, the sample size calculation was revised updating parameters of frequency of clinical improvement and dropout rate. The revised sample size is 180 participants randomly and equally divided into the two arms of the study (90 practitioners in each group).

The study consists of 3 periods: **screening, treatment, and follow-up.** In the screening period, patients who meet the eligibility criteria will be enrolled in the study and randomized into one of the two study arms, experimental or control. The first day of treatment will be day 1, and will last up to 14 days.

STUDY DESIGN

Treatment will be terminated early when two consecutive RT-PCR tests are negative (one of the criteria for hospital discharge). Treatment will also be stopped early in the event of participant dropout or in the event of an EAG.

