For Early Termination (ETA) of treatment, participants should follow the routine for visit 17: End of Treatment (D15), in advance. Discharge from the hospital may be

granted before the end of the 14-day treatment period if clinically indicated and the treatment has been completed.

The period between randomization and the end of treatment will be up to 14 days and there may be early termination (AT) or worsening. Participants who, even after the end of treatment, still remain in the hospital, will undergo the procedures and tests for safety and efficacy monitoring on D21 and follow the follow-up schedule from D28 to D60.

During the follow-up period, the participant will be required to return within 28 and 60 days of hospital discharge for follow-up visits.

The first day of treatment will be day 1 and will last up to 14 days.

Treatment will be terminated early when two consecutive RT-PCR tests are negative (criteria for hospital discharge) and may be stopped early in the event of participant dropout, or in the event of EAG.

All participants will undergo efficacy and safety evaluations. Blood samples and respiratory samples (oropharyngeal and nasopharyngeal swabs) will be obtained on days D1, D3, D5, D7, D9, D11, D13, and D14 (while hospitalized); and day D21 (participants still hospitalized after completion of treatment) and days D28 and D60 (upon return to the center or if still hospitalized). Detailed information about the visit is in section 7.3.

After discharge from the hospital, research participants should follow the instructions below in accordance with the care and attention specified by the research center:

- Stay in recovery for 3 to 6 weeks;
- Use face masks when necessary;
- Sanitize your hands and do not share personal objects;
- Avoid contact with people in the risk group, especially;

• Inform the Principal Investigator, or his/her team, immediately in case of fever and/or respiratory symptoms.

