VISIT 3-16: PROCEDURE (D1-D14)

The treatment period will start on D1 according to randomization.

The treatment will last up to 14 days, and may be stopped early in case of treatment success (2 consecutive negative RT-PCR tests), participant dropout, or at the Principal Investigator's option, if deemed necessary for the safety of the participant.

For the **Early Termination (ETA)** of treatment, participants should follow the routine from visit 17: End of Treatment (D15), in advance.

The Principal Investigator for the study will be available to answer any questions.

The experimental drug should be administered daily at 8 pm to minimize the risk of falling, since in preliminary studies, it was observed that vertigo (incidence ≥5%) appears to be an AE likely related to FNC. However, no restrictions on meals.

The following procedures will be performed in the V3-16 visits:

- Administration AZVUDINE or PLACEBO daily, at the same time at 8pm, to minimize the risk of falling, since in preliminary studies, it was observed that vertigo (incidence ≥5%) may be an AE likely related to FNC;
- Monitoring drug interactions and AEs on a daily basis;
- Monitoring symptoms, vital signs, oximetry and blood glucose daily;
- Collection of blood samples and respiratory sample (nasal and oropharyngeal swab) for safety and efficacy monitoring tests every 48h);
- CT scan of the lung every 4 days and electrocardiogram on days D1 and D11;

The Principal Investigator may adjust the procedures performed during treatment according to the condition of the research participant and the results of clinical examinations.

VISIT 17: END OF TREATMENT (D15)

At the end of treatment or discontinuation of the investigational drug or PLACEBO, all participants will be required to undergo procedures and tests for safety and efficacy monitoring. The procedures should be performed before discharge from the hospital approximately 24 hours after the administration of the last dose of the investigational drug or PLACEBO, because for the 5 mg dose of AZVUDINE, the mean half- life is 13.8 hours, and it is excreted in the urine within 24 hours.

The treatment will last up to 14 days, and may be stopped early in case of

treatment success (2 consecutive negative RT-PCR tests), participant dropout, or at the Principal Investigator's option, if deemed necessary for the safety of the participant.

The following procedures will be performed at the V17 visit:

- Monitoring drug interactions and AEs;

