8.1. SERIOUS ADVERSE EVENT (EAG)

According to ANVISA's definition, a serious adverse event is "one that results in any drug experience [...], occurring at any dose and resulting in any of the following outcomes."

- Death;
- Imminent threat to life;
- Persistent or significant disability/disability;
- Inpatient hospitalization or prolonged hospitalization;
- Congenital anomaly or birth defect;
- Any suspected transmission of an infectious agent through a drug;
- Other clinically significant events: events that can lead to one of the above, including but not limited to the following events, such as allergic bronchospasm requiring intensive treatment in the emergency room or at home, blood system cachexia or seizures not requiring hospitalization, potential drug-induced liver injury, spread of pathogens (non-pathogenic or pathogenic) via the study drugs, pregnancy, overdose, secondary tumors, etc, are generally considered serious, although they may not lead to death or hospitalization.

The Principal Investigator should provide the EAG severity criteria, based on the study protocol and their own medical judgment, on the eCRF and the results of the evaluation of the expected occurrence of the EAG and the correlation (cause and effect) with the study drug.

If the causality assessment performed by the Principal Investigator is missing or cannot be obtained, the sponsor will make the judgment and provide the final assessment, which will subsequently be confirmed by the Principal Investigator. If the Principal Investigator cannot determine whether or not the AE belongs to an SAE, then it will be considered an SAE until its nature is proven.

When any SAE occurs in the study, whether related to the experimental drug or not, the investigators should provide immediate assistance.

Planned or elective hospital admissions, for administrative reasons (such as annual physical exam) or prolongation of length of stay unrelated to worsening AEs, will not be considered SAEs. **The following situations will not be reported as SAE:**

- Treatments/procedures for a pre-existing condition/illness reported in the screening period;
- Hospital readmission due to the original disease with no new AE and no exacerbation of the original disease (such as verification of laboratory abnormalities that have persisted so far);

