9.4. DISCONTINUATION OR INTERRUPTION OF STUDY MEDICATION

If during the course of the study participants develop a more serious condition requiring intubation, considering that the drug is administered orally, the drug will be discontinued.

If during the course of this study participants exhibit any of the following criteria below, the Principal Investigator should judge whether they should discontinue their study medication:

- Confirmed by further examination, TBIL ≥B times the upper limit of normal value, ALT and AST ≥B times the upper limit of normal value;
- If the eGFR decreases to an eGFR <25 mL/min and the participant's renal function worsens to the point of requiring hemodialysis or hemofiltration;
- Any situation that, in the judgment of the Principal Investigator, puts the safety of the participant at risk.

Participants who discontinue study medication early should be encouraged to continue the post-treatment visit to continue safety and efficacy data collection despite discontinuation of study medication. Participants who agree to continue regularly scheduled study visits should complete the study termination assessments (V17) listed in the schedule of procedures detailed in Table 10 as close to the participant's last dose of study medication as possible. The visit data, including the primary reason for discontinuation of study medication, will be recorded in the eCRF. Subsequent study visit data, if applicable, will be recorded in the visit-specific eCRF, and the participant's final study visit will be recorded in the study termination eCRF.

If the reason for participants' discontinuation is an AE, they will continue to receive rigorous medical care until the clear outcome of recovery from AE or steady state. See Section 7 of this protocol for detailed follow-up information. For women who became pregnant during the trial period, the Principal Investigator can refer to item 4.9this protocol for treatment.

Participants discontinuing study medication who are unwilling to continue with regular study visits, but are willing to continue to provide their information for study use will be encouraged to remain in the study. The investigator will contact the sponsor's representative to determine the best approach based on the participant's situation, even if physical and laboratory examinations are not performed, monitoring for drug interactions and adverse events can be considered for such cases.

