11.2. STATISTICAL ANALYSIS POPULATION

- Full Analysis Set (FAS): a set of patients who were randomized and received at least one oral dose of the study drug.
- Per protocol set (PPS): a set of data generated by a subset of clinical trial subjects whose protocol compliance was strict, with no significant

deviation from the trial protocol, to ensure that the data are statistically relevant to answer the primary endpoint. PPS analysis will be used for the primary efficacy indicator.

 Safety data set (SS): a set of participants who have received at least one treatment, and have actual data recorded by the safety index after treatment. The SS analysis will be used for the incidence of adverse reactions.

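### The synopsis requires study drug to stop after a serious adverse event, other sections leave this to judgement, and a sentence in 9.1 fits neither the synopsis nor the protocol's other mandatory stops

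*Protocol*

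**What the plan says.** Several current passages of the protocol govern what happens to study drug after an SAE. The heading of section 8.1 shows that EAG means serious adverse event.

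- **Synopsis (1.1), study design:** "Treatment will also be stopped early in the event of participant dropout or in the event of an EAG".
- **Section 5.1.1:** treatment "may be stopped early in the event of participant dropout, or in the event of EAG". The same sentence uses mandatory wording for two consecutive negative RT-PCR tests.
- **Section 7.3 (treatment visits and Visit 17):** the reasons for early stopping are virological success, dropout, or the "Principal Investigator's option, if deemed necessary for the safety of the participant". An SAE is not listed.
- **Section 9.1, first paragraph:** "Treatment may also be discontinued if the Principal Investigator deems it best for the participant's safety".
- **Section 9.1, last paragraph:** the need for additional intervention and the occurrence of safety endpoints "are not criteria for withdrawal from the trial or the trial medication".
- **Section 9.4:** drug is discontinued if a participant needs intubation. For a short list of liver, renal and other safety situations, "the Principal Investigator should judge whether they should discontinue their study medication". An SAE as such is not on the list.
- **Section 8.9:** trial drug should be discontinued if pregnancy is discovered during treatment.

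Under 5.1.1, 7.3 and the second footnote to Table 10, a participant who stops early has the Visit 17 (D15) procedures in advance.

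**The concern.** A rule for stopping study drug on safety grounds should give one answer for one event. Here a reader of the synopsis would stop dosing at any SAE. A reader of 5.1.1, 7.3 or 9.4 would make a judgement. A reader of the last paragraph of 9.1 could conclude that the event gives no reason to stop.

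The first stake is the safe and uniform conduct of dosing. The second is measurement. The primary endpoint is improvement on the WHO scale up to D15, and the visit that closes the treatment period moves with the date of the last dose. Two participants with the same event can then have different exposure and a different assessment date, only because staff relied on different pages.

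**Working it through.** The protocol gives no figure on this point to reproduce, so the check sets the passages side by side.

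**1. Are SAEs covered by the 9.1 sentence?** It speaks of safety endpoints and does not name SAEs. Section 4 lists the frequency and intensity of serious adverse events as an outcome. Section 11.3 makes the occurrence of serious adverse events the dependent variable of the safety analysis under the primary goal. SAEs are therefore safety endpoints in the protocol's own terms. This is an inference, though a short one.

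**2. Three courses of action after an SAE, tested against each passage.**

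| Course | Synopsis | 5.1.1 | 7.3, 9.4 and first paragraph of 9.1 | Last paragraph of 9.1 |
|---|---|---|---|---|
| Dosing continues | breached | allowed | allowed if the investigator so judges | allowed |
| Investigator stops drug on a safety judgement | met | allowed | allowed | compatible, if the judgement and not the event is the ground |
| Drug stopped because an SAE occurred, with no further judgement | met | allowed | not provided for | denied as a criterion |

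The passages other than the synopsis can be read together as investigator discretion. The hard conflict is the mandatory wording of the synopsis against the rest.

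**3. The 9.1 sentence against the other mandatory stops.** Intubation is an additional intervention, and 9.4 makes it a reason to discontinue the drug. Section 8.1 lists pregnancy among events generally considered serious, and 8.9 calls for discontinuation when it is discovered during treatment. The 9.1 sentence, read as written, denies that either kind of event is a criterion.

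**4. Breadth of the trigger.** Under 8.1, an event whose seriousness the investigator cannot determine counts as an SAE until its nature is proven. The synopsis rule would therefore also reach events of uncertain seriousness.

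**5. Consequence for exposure and timing.** Inputs: 5 mg once daily for up to 14 days, so at most 5 × 14 = 70 mg (5.1.3); Visit 17 about 24 hours after the last dose (7.3). If the last of *k* daily doses is given on day *k*:

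- exposure = 5*k* mg;
- Visit 17 falls at about day *k* + 1, which is 15 − (*k* + 1) = 14 − *k* days before D15.

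For *k* = 7, exposure is 5 × 7 = 35 mg against up to 70 mg, and Visit 17 falls at about D8, 14 − 7 = 7 days early. For *k* = 14 it falls at D15, with no shift.

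**6. Frequency.** The protocol gives no expected SAE rate for this population, so no count of affected participants can be derived from it.

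**The case against.** The best defence is that these passages express one policy loosely worded: an SAE does not end treatment automatically, but the investigator may end it for safety. Sections 5.1.1, 7.3, 9.1 and 9.4 all fit that reading, and a participant stopped on a safety judgement satisfies every passage, including the synopsis. This much stands. It would be too strong to say that the synopsis, 5.1.1 and 9.1 are three mutually exclusive rules. The defence does not rescue the synopsis, which leaves no room for continuing, or the 9.1 sentence beside the intubation and pregnancy stops.

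It can also be said that follow-up after a stop is already planned. Visit 17 is required, 9.1 provides for D28 and D60, and 9.4 encourages later visits. That is true, but Visit 17 is the visit that moves forward and later attendance is only encouraged. A score at D15 is not secured.

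A reader might go further and infer that the contradiction changes the primary result through the per-protocol set, since 11.2 says "PPS analysis will be used for the primary efficacy indicator". The argument would run through adherence (6.7). A participant stopped after 7 doses scores 7/7 = 100% if doses fall due only up to the stop, but 7/14 = 50%, below the 80% limit, if all 14 remain due. The document does not support that step. Section 6.7 counts doses due within the dose administration period, treatment lasts up to 14 days, and nothing says that doses remain due after a permitted stop. Section 11.2 does not itemise significant deviations, and the statistical analysis plan may do so. No passage makes an investigator's safety stop after an SAE a deviation.

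**Conclusion.** The concern holds as a contradiction in a safety instruction. The synopsis mandates a stop that the operative sections leave to judgement, and the last paragraph of 9.1 conflicts with the synopsis and with two other stops in the protocol. It rests on current text, with one inference: that safety endpoints in 9.1 include SAEs. The intubation conflict does not need that inference.

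For an individual, the effect is a possible change in exposure and a shift of 14 − *k* days in the end-of-treatment assessment when dosing ends on day *k*. For the trial as a whole the size is unknown, because no SAE rate is given. An effect on per-protocol membership is possible, but it is not shown and should not be claimed. The correction should be made, because it is cheap and bears on participant safety.

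**What to change.** 1. The sponsor's clinical team reconciles the synopsis and sections 5.1.1, 7.3, 8.9, 9.1 and 9.4 into one consistent statement on study drug after an SAE, intubation and pregnancy, used identically wherever the subject arises. This review takes no view on which rule is right.
2. The protocol states that participants whose study drug is stopped for an SAE stay in follow-up and have the WHO score recorded to D15, in addition to the advanced Visit 17.

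The first change costs protocol wording and the approvals that section 10.9 requires for an amendment. The second adds WHO scoring between an early Visit 17 and D15 for the participants concerned. Neither change alters the sample size or the analysis model.
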